8.4 End of study

End of study occurs when all of the following criteria have been satisfied:

1. Thirty days after all patients have stopped protocol treatment
2. The trial is mature for the analysis of the primary endpoint as defined in the protocol
3. The database has been fully cleaned and frozen for this analysis

9 Trial Governance and Data Monitoring

9.1 Study committees

9.1.1 Study Management Group (SMG)

The Study Management Group is set up for this study. It consists of the EORTC Headquarters team in charge of running the study (clinical research physician, statistician, clinical scientist, clinical operations manager and data managers) and the principal study coordinator.

The EORTC Headquarter team is responsible for the day -to-day conduct of the trial. The Study Coordinator will assist the team in case of problems with patient evaluation (eligibility, treatment compliance, safety).

The Study management Group also performs the medical review as indicated below.

9.1.2 Study Steering committee (SSC)

The Study Steering Committee for this study is composed of the study coordinators, the representatives of Academic Groups collaborating to the study, at least one representative of the EORTC Headquarters (Study Clinical Research Physician or Clinical Scientist) and one representative of the Sponsor, if the sponsor is not the EORTC.

This committee provides the general oversight of the study and has the executive power. The SSC monitors study progress and conduct and advises on its scientific credibility. The SSC will consider and act, as appropriate, upon the recommendations of the independent data monitoring committee.

9.1.3 Independent data monitoring committee (IDMC)

The independent data monitoring committee for EORTC studies (IDMC) is in charge of the independent oversight of this study. The composition of the IDMC is described in EORTC Policy "Independent Data Monitoring Committees for EORTC studies" (ref. EORTC POL004) and its functioning is ruled by the charter annexed to the Policy.

The study-specific experts on the IDMC performing this review will be selected for their relevant expertise with the disease and/or treatments assessed in the study.

The IDMC reports its recommendations in writing to the Study Management Group through the clinical operations manager to the Study Steering Committee and other relevant parties (supporting bodies, collaborative groups...).

9.2 Data Monitoring

9.2.1 Monitoring during medical review meetings

The medical review will be performed on a regular basis by the clinical research physician assisted as needed by the study management group. The main study coordinator will, in particular, support the

Study Clinical Research Physician during the medical review process and will assist the team in case of problems with patient evaluation (safety, eligibility, treatment compliance). The main study coordinator is also responsible for the review and approval of the medical review plan and medical review reports.

For blinded trials, the medical review is conducted blinded to treatment allocation.

If at any time during the course of the study, the medical review identifies safety signals or other elements that could affect the potential risks and benefits to the study participants. These will be reported to the Study Steering Committee and may trigger a review by the EORTC Independent Data Monitoring Committee (IDMC).

9.2.2 Monitoring by the IDMC

The IDMC will be asked to give advice on whether the accumulating data from the trial justifies continuing recruitment of further patients or further follow-up.

The IDMC will review the trial whenever safety problems or other elements are identified during the medical review or by the SMG and/or SSC that could affect the potential risks and benefits for study participants.

The IDMC will also review the intermediate reports of accumulating data according to the study interim monitoring plan described in the statistical section of this protocol. If a decision is made to continue without change, the IDMC may advise on the frequency of future reviews of the data on the basis of accrual and event rates.

While the trial is ongoing the accumulating data will generally remain confidential, unless the SSC and IDMC agree that the data should be made public.

10 Quality of life assessment

Reducing mortality and morbidity is still the most important factor in clinical research. Nevertheless, issues such as reducing side effects, symptom relief and improving patients' satisfaction have also become relevant parameters in the evaluation of medical strategies. Cancer treatments may produce adverse effects and diminish the quality of life (QoL) even when survival is extended. Progress in the acceptance of new cancer therapies is sometimes critically dependent on their QoL consequences. Health related QoL is a multidimensional concept, which represents the physiological, psychological and social influences of the disease and the therapeutic process from the patients' perspective. It comprises four principal components: physical, psychological and social well-being, and daily-life functioning.

10.1 Rationale / objectives and hypothesis (background literature)

Patients with anaplastic glioma can have a poor QoL, but this has not been frequently assessed in large scale studies. It is highly likely that these patients will experience similar symptoms as recently reported in the 26951 and 26981 trials. That is, that patients can suffer from considerable levels of fatigue, have sleep problems, communication deficits, motor dysfunction and leg weakness with impairments in emotional and social functioning and express uncertainty regarding the future and an overall reduced QoL. Therefore, in this study, QoL is an important secondary endpoint. The main objective of QoL assessment within this clinical trial is to determine the impact of no adjuvant chemotherapy versus adjuvant therapy until progression for anaplastic glioma on overall health/QoL. Based on the recent EORTC study 26981, the hypothesis is that we expect no differences between arms using the global QoL scale during treatment, but there may be a later benefit to the adjuvant therapy arm if disease progression is achieved, thereby leading to a better global QoL. Several past neuro-oncological trials have shown an increased progression free survival after more intense initial treatment, without an effect on

overall survival. At present the impact of progression of high-grade glioma on the quality of life is not clear. It is not clear if increasing progression free survival is translated into a longer period with a better preserved quality of life. If that is the case, improvement of progression free survival would become a goal in itself. With this trial we will assess if QOL is decreased at the time of first progression, and if a longer progression free period is translated in a better QOL. To meet these objectives QOL questionnaires will also be administered after the first progression.

A secondary objective is to evaluate the effect of temozolomide on the various symptoms and functioning scales as treatment related side-effects may have a (temporary) negative influence on the health related domains of QoL of these patients. Based on the past study, we may see a slight increase in fatigue and reduction on social functioning in the adjuvant chemotherapy arm. However, once off treatment, we expect to see no differences

10.2 QL measures

Quality of life will be assessed with the EORTC Quality of Life Questionnaire (QLQ-C30) version 3. This is composed of multi-item and single scales. These include five functional scales (physical, role, emotional, social, and cognitive), three symptom (fatigue, nausea and vomiting and pain) and a global health status/QOL scale and six single items (dyspnea, insomnia, appetite loss, constipation, diarrhea and financial difficulties). All scales and single items meet the standards for reliability. The reliability and validity of the questionnaire is highly consistent across different language-cultural groups [Aaronson et al., Ref. 26]. While this standard is used in EORTC studies, it lacks some dimensions that pertain to the QL issues in certain cancers in brain cancer. Therefore we will use the EORTC Brain Cancer module (QLQ-BN20) is designed for use with patients undergoing chemotherapy or radiotherapy. It includes 20 items assessing: visual disorders, motor dysfunction, communication deficit, future uncertainty, as well as other specific symptoms, such as headaches, seizures or drowsiness). A validation study has been performed with English-speaking patients from Canada, the UK and the USA. (Osoba et al 1996, Ref. 27). An additional validation analysis is planned and will be completed within the time frame of this clinical trial.

10.3 Study design

Patients are eligible for the quality of life assessment in this study if they fulfill the eligibility criteria (Chapter 3) and, more importantly, complete the baseline quality of life questionnaire before randomization. Given the important of QOL in this study, being able to provide a completed QOL form is an important eligibility criterion. Of course, should the QOL forms not be available in the required language then this should not exclude the patient from participating in the study. Patients will be informed in the patient informed consent form that they will have their quality of life assessment regularly while involved in this trial. QoL will be a secondary outcome and evaluated in a longitudinal design for in all patients entered in this study.

10.3.1 QoL data collection - Timing and where and how

QoL questionnaires must be filled out at the hospital when the patient comes for a scheduled visit. The questionnaire will be handed out to the patients by the investigator or a study nurse prior to seeing the doctor for clinical evaluations. Patients will be asked to fill out the questionnaires as completely and accurately as possible. The average time to complete the entire questionnaire is approximately 10-15 minutes. Master copies of the QoL questionnaires (EORTC QLQ-C30 and the QLQ-BN20) will be sent to the institution together with the CRFs. The clinical forms will include a question whether the QoL forms have been filled in -and if not, the reason why. Data collection procedures should be followed using the EORTC guidelines in Appendix D. Time windows for eligible follow-up assessment will be (+/-) 3 weeks the scheduled follow-up assessment.

The questionnaire should be completed within 14 days prior to randomization, then at 4 weeks off radiotherapy, then at every 3 monthly visit. After treatment discontinuation of treatments, QoL measurements are carried out every six months, at each follow-up visit up during coming five years or death if it occurred earlier. Even if patient's progress, QOL forms should still be collected every six months until death.

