6.4.1 Six monthly disease evaluation after the end of radiotherapy

All patients would have six monthly disease and status assessment after the end of radiotherapy.

- Physical examination including neurological evaluation
- Corticosteroid intake
- MMSE
- Quality of Life C30 and BCM20
- WHO-ECOG performance status
- Toxicity according to CTCAE v.3
- Gd-enhanced MRI or contrast CT scan of the brain
- Cognitive exam; dedicated centers only, to be carried out yearly after the start of radiotherapy (e.g., 12 months, 24 months, 36 months etc)

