6.5 After the documentation of first progression

The patient must be followed every six months, in particular for performance status, quality of life, cognition and for documentation of further treatments.

- Physical examination including neurological evaluation
- Corticosteroid intake
- MMSE
- Quality of Life C30 and BCM20
- WHO-ECOG performance status
- Documentation of further treatments

All patients will be followed until death.

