10.4 Statistical considerations

The sample size calculation has been performed based on overall survival data. This is the primary endpoint and therefore no calculation has been performed based on changes in QL. The primary QL endpoints that are considered relevant to this trial are global QOL. The QOL data will inform the hypothesis that we expect no differences between arms using the global QOL scale during treatment, but there may be a later benefit to the adjuvant therapy arm if disease progression is achieved, thereby leading to a better global QOL. Hence, the global quality of life scale of the QLQ-C30 will be used as the primary QL outcome of interest. Based on the work of Osoba et al. (Ref. 27), a difference of 10 points on a 100 point scale between the two treatment arms will be considered as clinically significant. The standard deviation of the global QoL scale is approximately 20 points. With a minimal effect size of 0.5 (i.e. one-half standard deviation), with alpha set at 0.5 and beta at 0.20 (power 0.80), a minimum of 64 patients per treatment arm is required. The other scales of fatigue and social functioning will be analyzed as secondary QOL endpoints. The remaining scales will only be analyzed on an exploratory basis. Data will be scored according to the algorithm described in the EORTC QLQ-C30 scoring manual. All scales and single items are scored on categorical scales and linearly transformed to 0-100 scales where:

A high score for a symptom scale or item represents a high level of symptoms or problems.

A high score for a functional scale represents a high or healthy level of functioning.

A high score for the global health status/QoL represents high QoL.

When performing a QoL analyses complications may arise due to large quantities of missing data. This issue has a bearing on whether a valid comparison of the treatment arms is being made.

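### Section 10.3.1 contradicts chapter 6, and itself, on when QoL collection ends; followed literally, it would select the forms at about years 5.1-6.1 by arm and progression status

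*Combined protocol and SAP*

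**What the plan says.** Two parts of the protocol set the end of QoL collection.

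- **Section 10.3.1.** "After treatment discontinuation of treatments, QoL measurements are carried out every six months", and they continue "at each follow-up visit up during coming five years or death if it occurred earlier". The clock starts when treatment stops. The next sentence reads: "Even if patient's progress, QOL forms should still be collected every six months until death".
- **Chapter 6.** Section 6.4.1 states: "All patients would have six monthly disease and status assessment after the end of radiotherapy". Its list includes both QoL questionnaires. For the time after first progression, section 6.5 states: "The patient must be followed every six months, in particular for performance status, quality of life, cognition", and closes with: "All patients will be followed until death". The summary table in 6.6 agrees. None of these has a five-year limit or a clock that depends on the arm.

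Section 8.2.3.5 refers the QoL analysis to chapter 10, but no text says which schedule governs collection. The main QoL hypothesis in 10.4 is that "there may be a later benefit to the adjuvant therapy arm", with no time point for that later benefit. The same section plans mean scores by arm at each assessment, and a mixed model if missing data are judged ignorable.

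**The concern.** Section 10.3.1 conflicts with itself (five years against until death) and with chapter 6 (no limit). Read literally, it makes the length of collection depend on two things that should not decide who contributes to a between-arm comparison: whether the patient has progressed, and when treatment ended. Treatment ends later by design in arms 3-4.

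Between the two limits, the arms would be represented by different kinds of survivor. Arms 1-2 would send forms only from patients who had progressed, and arms 3-4 from both progressed and progression-free patients. A difference in arm means at those visits would partly reflect who was asked to fill in a form. The QoL hypothesis concerns a late advantage of adjuvant treatment, so the distortion could be mistaken for the effect being sought. The compliance comparison in 10.3.2 might not show it, because a form that is not due need not count as missing (an inference, not something the protocol states).

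The three-monthly visits mentioned in 10.3.1 against the six-monthly schedule of chapter 6 are a separate matter.

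**Working it through.** The plan gives no figure on this point to reproduce. The check is calendar arithmetic under the literal reading of 10.3.1, followed by a two-group mixture.

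**Inputs from the protocol.** Radiotherapy (RT) lasts 6.5 weeks (5.2.1) and starts 0 to 8 days after randomization (3.2). Rest is 4 weeks, then at most 12 cycles of 28 days (5.2.2.4). The QoL visit window is 3 weeks either side (10.3.1). One year is 365.25/7 = 52.18 weeks.

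**Step 1: the two limits, in years from randomization.**

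- Arms 1-2: 5 + 6.5/52.18 = 5.12, or 5.15 if RT starts on day 8.
- Arms 3-4, 12 cycles, counted to the end of cycle 12: 5 + (6.5 + 4 + 48)/52.18 = 6.12, or 6.14. Counted to the last dose (4 + 44 + 5/7 weeks after RT): 6.06 to 6.08.
- Offset for c cycles: (4 + 4c) × 12/52.18 months. This gives 12.0 months at 12 cycles (11.2 to the last dose), 6.4 at 6 cycles and 3.7 at 3 cycles.

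**Step 2: the forms affected, numbered in months after RT as in 6.4.1.** The limit falls at 60 months in arms 1-2. In arms 3-4 it falls at 60 + 11.2 to 12.0 = 71.2 to 72.0 months with 12 cycles, 66.4 with six and 63.7 with three. The 66-month form is clearly affected for patients given about six cycles or more. The 72-month form sits on the limit, within the visit window, so it is borderline.

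**Step 3: effect on raw means.** Let f_C and f_A be the progression-free share of survivors without and with adjuvant temozolomide, and D the QoL gap (progression-free minus progressed). None of these is in the documents. Section 10.1 says the impact of progression on QoL is not clear. The assumed ranges are 5-20 points for D and 30-70% for the shares.

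- Difference if everyone is measured: (f_A − f_C) × D.
- Only the arms 1-2 limit has passed: observed f_A × D, so bias = +f_C × D.
- Both limits have passed: observed 0, so bias = −(f_A − f_C) × D.

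| Period from randomization | D = 5 | D = 10 | D = 20 |
|---|---|---|---|
| Before about 5.1 years | 0 | 0 | 0 |
| About 5.1-6.1 years, f_C = 0.3 to 0.7 | +1.5 to +3.5 | +3 to +7 | +6 to +14 |
| After about 6.1 years, f_A = f_C | 0 | 0 | 0 |
| After about 6.1 years, f_A − f_C = 0.10 | −0.5 | −1 | −2 |

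Positive values favour adjuvant temozolomide. Section 10.4 treats 10 points between arms as clinically significant.

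**Step 4: how many patients.** With the design medians in 8.1.1, exponential survival and 748/4 = 187 per arm, expected survivors at 66 months are:

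- no adjuvant: 187 × (2^(−66/24) + 2^(−66/31)) = 71
- adjuvant: 187 × (2^(−66/31) + 2^(−66/40)) = 102

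Under the literal cap, arms 1-2 would contribute only their progressed survivors: 71 × 0.3 to 0.7 = 21 to 50.

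The survival assumption matters. At 5.1 years (61.2 months) the 24- and 31-month medians give 2^(−61.2/24) = 17% and 2^(−61.2/31) = 25% alive. A constant hazard from the two-year rates in 8.3.2 gives 0.719^2.55 = 43% and 0.747^2.55 = 48%, but those rates describe the concurrent comparison at the futility boundary. All these figures count every survivor, whereas the cap touches only those still progression-free.

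**Step 5: after the fix.** With one horizon for all patients the offset is 0 months and this bias is 0 points.

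**The case against.** The strongest reply is that chapter 6 is the visit schedule and has no cap. Sites that followed it collected QoL from everyone, and no selection arose. The sentence in 10.3.1 about progression may mean only that progression does not end collection. This stands in part: a reader might infer that forms really did stop by arm and progression status, and the documents do not show that. It does not clear the text. Until death still conflicts with five years, and a cap applied to everyone would still run from the end of treatment, so the horizon would still differ by arm.

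Three further points stand:

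- A reader might infer that late QoL comparisons in general lean toward adjuvant temozolomide. They do not. The later benefit in 10.4 is set against the period during treatment, so it covers follow-up from about 13.5 months on (6.5 + 4 + 48 = 58.5 weeks), nearly all of it before the window. Past about 6.1 years the tilt is gone or reversed.
- A full year's offset is the maximum, because adjuvant treatment may stop early (5.2.2.4, 5.3, 5.4).
- The raw-mean calculation does not show bias in the modelled analysis. Section 10.4 calls the by-arm means descriptive and provides mixed, selection or pattern-mixture models. A mixed model may reduce the effect, but the plan does not say that progression status enters it, so removal cannot be relied on.

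**Conclusion.** The point holds as a contradiction on when QoL collection ends, with a clock tied to the end of treatment and therefore to the arm. The conditional consequence is limited: if 10.3.1 was followed literally, the forms between about 5.1 and 6.1 years are selected by arm and progression status. That is one clear six-monthly form, at 66 months, with 72 months borderline.

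The size, +1.5 to +14 points on raw means, rests on assumed values for the progression gap and the progression-free share. The direction requires worse QoL after progression, which the protocol leaves open. The documents do not support a claim that the plan manufactures a late benefit: whether forms stopped is unknown, and the effect on the modelled comparison is not shown. This is a secondary endpoint, and the repair is cheap enough that it should be made.

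**What to change.** 1. Reconcile 10.3.1 with sections 6.4.1, 6.5 and 6.6 so that one QoL horizon applies, the same in all arms and regardless of progression.
2. State in 10.4 that, where forms were collected under the cap, between-arm QoL comparisons use visits up to five years from randomization and later forms are described only. RT starts after randomization, so five years from randomization comes before any limit counted from the end of treatment.

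The cost is one sentence in each section. Late forms collected under the cap are lost to comparison. This includes the form due 60 months after RT, which falls at about 61.5 months from randomization (60 + 6.5 × 12/52.18) and sits on the arms 1-2 limit. The last form clearly inside is the one at 54 months after RT. Appendix M says enrolment and treatment are complete, so it is worth establishing first which schedule sites followed. If they followed chapter 6, the restriction in item 2 is not needed and the late forms can be kept.

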10.3.2 Compliance

Missing data may hamper assessment of QL in clinical trials. This may be because centers do not collect the questionnaires at the appropriate time (unit non-response), and because patients may miss questions within the questionnaires (item non-response). The latter problem occurs less than 2% on average and should not be a problem. The former problem will be minimized by ensuring that participating centers are properly informed and motivated towards QL assessment.

During the study, compliance with completing QoL questionnaires will be investigated at each time point. The compliance of the QoL assessments will also be reviewed twice a year and will be a part of the descriptive report by the EORTC Headquarters for the Group's plenary sessions. Having high compliance is imperative to this QOL study and all reasonable attempts to collect QOL data must be made. The compliance data by institutes should be presented to the entire group in order to help identify centers that are struggling to obtain maximum QOL compliance levels and efforts to improve this should be included as corrective methods (e.g. Education to nurses and doctors about the importance of the data and how to collect it)

The compliance rate between the 2 arms will be compared at each time point using a chi-square test. In order to adjust for the multiplicity of the tests, a Bonferroni adjustment will be made by which each test will be performed at the 0.01 significance level. Should serious volumes of missing questionnaires occur then the protocol writing committee would review the QL assessment in the trial. If compliance levels fall below 70% at any time point protocol writing committee would need to take remedial action to improve the position.

